## Safety Reporting

### *Adverse Events (AE)*

For work packages 2 and 3 adverse events will be monitored and recorded. Adverse events (AEs) are any clinical change, disease or disorder experienced by the participant during their participation in the trial, whether or not considered related to the use of treatments being studied in the trial. Any adverse events that occur will be recorded in an Adverse Event Log, designed for this study, and the service user's clinical records, if appropriate. The service user will be followed up by the research team to ensure the event is resolved.

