## **Why DIALOG+ needs to be adapted for people with ID**

DIALOG+ has not been used or evaluated in people with ID. Feedback from service users with ID and clinicians who we have engaged with, have been positive about the potential for DIALOG+ to facilitate improved communication between clinicians and service users. One service user commented "it's important that professionals ask the right questions about what is important to me". DIALOG+ could empower individuals with ID to engage in meaningful conversations, promoting a greater sense of control and agency, potentially leading to improved QoL and fewer behaviours that challenge. However, they emphasised that the existing intervention is not accessible for this population (e.g. language/ response format of the DIALOG scale/ supporting app is too complex and the QoL domains are not all relevant. Evidence from the literature suggests that quality of life domains such as autonomy and rights are important for people with ID but the existing DIALOG scale does not include these domains (26-27).

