## Study Design

### 1. Work package 1a: Piloting adapted DIALOG+

The adapted DIALOG scale and intervention (aDIALOG+) will be piloted with five clinicians (any background e.g. nurse, occupational therapist, psychiatrist, social worker) from community ID teams in the East London NHS Foundation Trust (ELFT) and five care workers. Clinicians will be eligible if they are aged 18 or over, are currently working within a community ID service, intensive support team or in a local authority or social care organisation for people with ID, are from any profession (e.g. psychology, nursing, speech and language therapy, psychiatry, social work) at grade 4 and above with a minimum of six months experience working with people with ID, and consent to participate. Care workers will be eligible if they are aged 18 or over, have worked in the care home for at least three months, provide at least one day of support per week to service users, and consent to participate. Clinicians and care workers will receive training on how to deliver aDIALOG+ and will receive a copy of the manual, and an electronic tablet to enable them to access the app. The tablet will be insured and it will be the research team's responsibility to provide replacements. Clinicians and care workers will be asked to administer the aDIALOG+ intervention using the app (at least once) to two service users each (20 service users in total).

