For clinical services, eligible service users with ID will be identified from the case load of the participating clinician through the review of medical records. They will then be approached by the participating clinician or Clinical Studies Officer (CSO) to take part in the study and an information sheet will be provided. For care homes, eligible service users with ID will be identified from service records / clinical notes by care workers, and the research team will ask staff to approach eligible service users to take part in the study. If they are interested, their details will be passed to the research team, who will contact the potential participant, provide an information sheet, and assess their eligibility and capacity to consent. Service users will be eligible if they are aged 18 or over, have mild or moderate ID based on service records / clinical notes, have a current history of behaviour that challenges (at least one incident of self-injurious behaviour, physical aggression or damage to property in the last 3 months), are living in any setting including the family home and supported living/ residential home, and can provide informed verbal or written consent. We will ask clinicians and care workers to identify and approach all the service users on their caseload or within the care home, who are potentially eligible to take part, to take part in the study until they reach the recruitment target. This should reduce the likelihood of clinicians and care workers only approaching certain individuals to take part.

After 4-6 weeks we will invite the five clinicians, five care workers and at least ten service users to take part in separate stakeholder focus groups or interviews to obtain feedback on what aspects of the intervention (including the aDIALOG scale, app, training and manual) that worked well or did not work well and suggestions for improvement. Topic guides for the focus groups/interviews will be developed with input from the adaptation group (group of clinicians, carers and service users overseeing the work). We will also ask clinicians and care workers to complete the NoMAD questionnaire (39) for assessing implementation processes.

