**Table 1: ICONIC WP1a Piloting screening and data collection schedule**

	Completed by	Storage	Pre-consent	Consent	4-6 weeks	Ongoing or during intervention
Clinicians and care workers screened for eligibility	RT / CSO	DSH	x			
Clinician and care workers consent form	C / CW / RT / CSO	LC		x		
Service users screened for eligibility	C / CW	DSH	x			
Service users consent form	SU / RT / CSO	LC		x		
aDIALOG+ app data	SU / C / CW	ET				x
Participant withdrawal CRF	RT / CSO / SU / C / CW	LC				x
Focus group / interview audio recordings and transcripts	SU / C / CW / RT / CSO / TC	DSH			x	

NoMAD questionnaires	C / CW / RT / CSO	LC				x	
----------------------	-------------------	----	--	--	--	---	--

*Key: CW = care worker; C = clinician; CSO = clinical studies officer; DSH = data safe haven; ET = encrypted tablet; LC = (locked cabinet on ELFT property); RT = research team; SU = service user; TC = transcription company*

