Statistical analysis (work package 1b): We will examine the distribution, variability and mean/median scores for each of the items. In order to assess concurrent and convergent validity, we will examine spearman's correlation between the items relating to subjective quality of life on the aDIALOG scale and the other measures. We will assess test re-test reliability by calculating the intra class correlation coefficient (ICC). Items that show poor distribution, variability and poor test re-test reliability may be removed from the scale. We will measure the internal consistency of the items relating to subjective quality of life and the treatment aspects separately using Cronbach's alpha.

Statistical analysis (WP 2 and WP 3): The feasibility outcomes will be the main focus of analysis and descriptive statistics, with associated measures of precision appropriately accounting for clustering, will be used to assess recruitment and retention, adherence, response rates in completing the outcome measures, demographic and clinical data, and cost data. We will explore changes in the scores of the outcome measures using paired t-tests or non-parametric tests where appropriate. The primary outcome measure of changes in behaviour will be measured using the Aberrant Behaviour Checklist (ABC)- irritability subscale (43). For secondary outcomes we will measure changes in behaviour (Behaviour Problems Inventory- short form) (53), quality of life (WHOQOL Disabilities module) (40), community participation (Guernsey Community Participation and Leisure Assessment – Revised) (44), psychological distress (Clinical Outcomes in Routine Evaluation, 14 item version) (42), psychiatric disorders (Moss Psychiatric Assessment Schedule - Check) (45), global improvement (Clinical Global Impression Scale) (46), health related quality of life (modified version of the EQ-5D-3L for people with ID) (48, 49) and service use (the Client Services Receipt Inventory) (51). The frequencies of adverse and serious adverse events will also be reported.

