## **9 ETHICAL AND REGULATORY CONSIDERATIONS**

### **9.1 Assessment and Management of Risk**

We do not anticipate any unintended consequences/ adverse events. Safety concerns will be discussed with the study steering committee and the ethics committee will be informed if necessary. This may lead to termination of the study or the study may be paused until the issue is investigated. As this is a feasibility study, there will not be a data monitoring committee.

It will be explained to all participants that participation is voluntary, that they can withdraw at any time without providing an explanation, and that their care will not be affected if they do not participate in the study. Baseline and follow-up assessments will be conducted face-to-

face where possible but we will accommodate remote assessments if participants express a preference. Assessments may be carried out in clinic settings or in service user's homes based on their preference. We have kept the number of measures to a reasonable number in order to reduce burden on service users and carers, and where possible we have used short versions of measures. We will provide £20 gift vouchers to service users and carers to thank them for their time for completing qualitative interviews and after the baseline assessment and prior to the follow-up assessments.

To maintain participant and researcher safety, we will ensure that risk assessments are conducted prior to meeting the service user, especially if they are going to be seen in their home. This will involve reviewing existing risk assessments, and if one is not available, researchers will seek information from the referrer. If there is a potential risk of physical aggression to researchers, each case will be discussed with their line manager / supervisor and arrangements will be made to ensure risks can be mitigated (e.g. carrying a personal alarm, ensuring service user is seen with their carers). Lone working policies will be followed for home visits.

If service users become distressed during their aDIALOG+ sessions or during end of study interviews, sessions will be stopped or service users will be offered a break and given the option of continuing or rescheduling the session. We will discuss concerns with the service user's clinical team.

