## 12.2 Appendix 2 – WP1a and b Schedule of Procedures

Procedures	1	2	3	4	5	6	7	8	9	10	11	12	13	14	15	16	17	18
	Jun 25	Jul 25	Aug 25	Sep 25	Oct 25	Nov 25	Dec 25	Jan 26	Feb 26	Mar 26	Apr 26	May 26	Jun 26	Jul 26	Aug 26	Sep 26	Oct 26	Nov 26
Recruitment of clinicians and care workers	x																	
Clinician and care worker training in aDIALOG+	x																	
Recruitment of service users		x																
Delivery of aDIALOG+ intervention		x																
Stakeholder focus groups/ interviews			x															
Data analysis and adaptations				x														
Recruitment of service users	x	x	x	x	x	x												
Baseline data collection	x	x	x	x	x	x												
Follow up	x	x	x	x	x	x												
Data analysis							x	x										

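### Non-serious adverse events in the 20 work package 1a service users, the first to receive aDIALOG+ under this protocol, have no planned study record

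*Protocol*

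**What the plan says.** Under Safety Reporting, the subsection on adverse events begins "For work packages 2 and 3 adverse events will be monitored and recorded". The definition of an adverse event and the Adverse Event Log follow under that sentence. In Data Storage and Analysis, the paragraph on WP2 and WP3 adds "The frequencies of adverse and serious adverse events will also be reported"; the paragraph on WP1b has no counterpart, and WP1a has no statistical analysis paragraph.

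WP1a delivers the intervention. Its design section says "Clinicians and care workers will be asked to administer the aDIALOG+ intervention using the app (at least once) to two service users each", which makes 20 service users. The Background states "DIALOG+ has not been used or evaluated in people with ID". Feedback comes later: "After 4-6 weeks we will invite the five clinicians, five care workers and at least ten service users to take part" in focus groups or interviews.

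Section 9.1 foresees that sessions can upset people: "If service users become distressed during their aDIALOG+ sessions or during end of study interviews, sessions will be stopped", or the person is offered a break, and concerns are discussed with the clinical team. That text names no work package and sets out no study record of the event.

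Two other provisions also apply without naming a work package. The subsection on serious adverse events requires every such event to be logged on a case report form, and section 9.1 requires safeguarding incidents to be recorded.

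**The concern.** A pilot in a new population is where unexpected harm should first become visible. Here the recording rule runs the other way: the later recipients have a log for non-serious events, the first recipients do not, and the protocol gives no reason.

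WP1a exists to find out what must change before WP2 and WP3. Its timetable includes a step called "Data analysis and adaptations" in September 2025, just before the later packages start delivery. Section 9.1 also allows safety concerns to pause or end the study. As written, neither the adaptation step nor that decision would have a systematic account of non-serious events from the pilot. Both would rely on what deliverers and interviewed service users recall and choose to raise.

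**Working it through.** **Who receives aDIALOG+.** WP1a has 5 clinicians and 5 care workers with two service users each: (5 + 5) × 2 = 20, which reproduces the total in the WP1a design section and in section 7.2.1. WP2 plans 30 and WP3 approximately 40. All recipients: 20 + 30 + 40 = about 90. Inside the adverse-event scope: 30 + 40 = about 70. Outside it: 20, and 20/90 = 22%. WP1b completes the scale and other questionnaires but does not receive the intervention, so it is not counted.

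**Whether they are a different kind of participant.** Section 7.1.1 gives WP1a, WP2 and WP3 the same criteria on age, severity of intellectual disability and recent behaviour that challenges. Nothing there marks WP1a users as lower risk.

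**Order of delivery.** The schedule in section 12.2 puts WP1a delivery in July 2025, focus groups and interviews in August, and analysis and adaptation in September. Sections 12.3 and 12.4 start WP2 and WP3 delivery in October 2025. A WP1a log read in September would therefore arrive in time to be used.

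**What is recorded, by work package.**

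| Type of event | WP1a | WP2 and WP3 |
|---|---|---|
| Non-serious adverse event | No planned study record | Adverse Event Log |
| Serious adverse event, in text | Logged on a case report form (no package limit) | Same |
| Serious adverse event form in data schedule | Not in Table 1 | In Tables 3 and 4 |
| Safeguarding incident | Recorded (no package limit) | Recorded (no package limit) |
| Distress that stops a session | Managed; no record stated | Managed; logged only if it counts as an adverse event |
| Session recordings in data schedule | Not in Table 1 | In Tables 3 and 4 |

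**Reading the schedules.** "Table 1: ICONIC WP1a Piloting screening and data collection schedule" has eight rows. One is a withdrawal form; none is a safety form. The missing adverse-event log row proves nothing by itself, because Tables 3 and 4 have no such row either. The missing serious adverse event row does count: the text logs all serious events, but the WP1a schedule provides no form for them.

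**Whether the definition catches distress.** The protocol defines an adverse event as a clinical change, disease or disorder during participation, whatever its cause. Upset that ends a session and passes after a break does not clearly meet that definition in any package. Adding WP1a to the scope sentence would therefore not be enough to capture it; a separate statement is needed, and it should apply to WP2 and WP3 as well.

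**The case against.** The best case for leaving the plan alone is proportionality. WP1a is a small qualitative pilot of a conversation-based intervention that need be delivered only once, whereas WP2 and WP3 run monthly sessions for six months. Lighter recording of minor events is a defensible choice, and no other part of the protocol contradicts it. Information also has other routes. All ten deliverers, who between them see all 20 users, are invited to say what did not work well. The research team is in regular contact with them (section 7.3.2). Safety concerns in any package go to the steering committee. A log of in-session distress would itself be filled in largely by the same deliverers.

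Much of this stands, and it keeps the point small. It does not remove it. Feedback after 4-6 weeks is recall, not a record made at the time, and the WP1a feedback questions concern what worked and what to improve. WP2 interviews, by contrast, ask expressly about unintended consequences. Stopping a session looks after the individual but leaves the study with no entry.

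A reader might infer that the 20 users have no adverse-event record of any kind. The protocol does not support that: serious events, including those an investigator judges medically significant, and safeguarding incidents are recorded in every package. A reader might also infer that distress among users who are not interviewed would go unheard. That does not follow either, because each of those users has a deliverer who is invited to give feedback. Nor can a likely number of missed events be given: the protocol states no rate of distress or adverse events, and its intracluster correlation of 0.04 is offered for recruitment and retention, not for harms.

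**Conclusion.** The point holds in a narrow form. Non-serious adverse events in the 20 WP1a service users, 22% of about 90 planned recipients and the first under this protocol, have no planned study record. For serious events there is a smaller mismatch between the text, which logs them all, and Table 1, which has no form for them.

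The 22% assumes that WP2 and WP3 reach their planned 30 and approximately 40 service users. The point about sequence assumes that delivery follows the schedules in sections 12.2 to 12.4. No estimate, test or sample size is affected, and WP1a has no quantitative safety objective. What changes is the safety information available before the later packages begin. This is a cheap improvement, not a flaw that threatens the study's conclusions.

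**What to change.** 1. Extend the opening sentence of the adverse-event subsection so that monitoring and recording cover work packages 1a, 2 and 3, using the same Adverse Event Log over the 4-6 weeks of WP1a.
2. State for all three packages that any aDIALOG+ session stopped because of distress is entered in the log, since the present definition may not capture it.
3. Add a serious adverse event form row to Table 1, in line with the text and with Tables 3 and 4.
4. Review the WP1a entries at the September 2025 analysis and adaptation step, before WP2 and WP3 delivery begins.

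WP1b can stay outside, as its participants complete questionnaires only.

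The cost is modest. The log is already planned but must be ready for July 2025 and not October 2025. Ten deliverers take on a small recording task for 20 users over 4-6 weeks, and some entries will be low-grade.

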### *Serious Adverse Events (SAE)*

A SAE is defined as an untoward occurrence that:

- a) Results in death
- b) Is life-threatening
- c) Requires hospitalisation or prolongation of existing hospitalisation
- d) Results in persistent or significant disability or incapacity
- e) Consists of a congenital anomaly or birth defect or
- f) Is otherwise considered medically significant by the investigator.

An SAE occurring to a research participant should be reported to the Sponsor and REC wherein the

local PI deems the event:

- Related- that is, resulted from administration of any of the research procedures and
- Unexpected- that is, the type of event is not listed in the protocol as an expected occurrence.

Hospitalisation will not be reported if it is for routine treatment, treatment which was elective or preplanned, hospitalisation for general care where there was no deterioration in condition, or treatment on an emergency outpatient basis for an event not fulfilling any of the definitions of serious as given above, and not resulting in hospital admission.

SAEs that are related and unexpected will be reported to sponsor within 24 hours and to the main REC within 15 days of learning of the event.

All SAE's will be logged via a SAE Case Report Form that will be completed by a local researcher and signed and dated by the local Principal Investigator.

### *Urgent Safety Measures*

In the case of urgent safety measures being required, the CI will inform the sponsor and the REC of the event immediately via telephone. The CI will then inform the REC and the Sponsor in writing within 3 days.

### *Annual Safety Reporting*

If required by the REC, the CI will send the Annual Progress Report to the main REC using the HRA template and to the sponsor.

### *Overview of the Safety Reporting Responsibilities*

The CI will ensure that safety monitoring and reporting is conducted in accordance with the sponsor's requirements.

### *Central Monitoring*

For work packages 2 and 3 the programme manager will carry out central monitoring of recruitment rates and every 3-4 months review required documentation for sites (e.g. delegation logs) and data completion.

### *Audits*

The Sponsor or delegate retains the right to audit any study, study sites, or central facility. Any part of the study may be audited by the regulatory bodies, and funders, where applicable. The TMF will be audited once at minimum by PCTU.

## **9.2 Research Ethics Committee (REC) and Other Regulatory Review and Reports**

The CI ([name]) will ensure that the study is carried out in accordance with the ethical principles in the UK Policy Framework for Health and Social Care Research.

As this study involves NHS service users and is being conducted in England, before the study starts it will require approval from the Health Research Authority (HRA) and a favourable opinion from the REC for the study protocol, informed consent forms and other relevant documents, e.g. information sheets, topic guides etc.

Any substantial amendments requiring review by the REC will not be implemented until a favourable opinion has been granted and approved by the relevant NHS R&D departments and HRA. The CI will ensure that an annual progress report is submitted to the REC within 30 days of the anniversary date on which the favourable opinion was granted. The annual report will be submitted each year until the study is declared ended.

The CI will notify the REC, HRA and study sponsor of the end of the study, and will immediately notify the REC, HRA and study sponsor should the study end prematurely. This will include notification of the reasons for premature termination.

## **Regulatory Review and Compliance**

The Chief Investigator will ensure that appropriate approvals from participating organisations are in place. Specific arrangements to gain approval from participating organisations will comply with the Health Research Authority's Assessment Criteria and Standards Document. Once informed, organisations will be given 35 days to object to the approvals based on their resources. For example, the institution may object if it does not have eligible staff members for participation. Then the study may commence without institutional confirmation if not forthcoming.

